3. STUDY OBJECTIVE

The primary objective of the study is to assess Cardiac Output Monitoring in pediatric subjects by comparing FloTrac, ClearSight and the Fick principle (using Swan Ganz) to intermittent thermodilution Swan-Ganz, in order to expand the indications of FloTrac, ClearSight and Swan-Ganz thermodilution pulmonary artery catheter to the pediatric population 12 to 18 years of age.

Study Endpoints

The primary effectiveness endpoint is to demonstrate that monitoring of cardiac output (CO) with Swan-Ganz, FloTrac, and ClearSight is comparable as determined by the Bland-Altman method of bias.

The primary safety endpoint is to assess all serious intraoperative and post-operative adverse events through 30 days, including serious device-related events.

The secondary effectiveness endpoint is to demonstrate that monitoring of cardiac output (CO) with Swan-Ganz, FloTrac, and ClearSight is comparable as determined by the Critchley and Critchley method of percent error calculation.

POGO Study		
Study #2019-08		

4. STUDY DESIGN

General Design

This study is an observational study in the U.S. Up to 108 eligible Subjects will be enrolled at up to five (5) study sites. A subject will be considered enrolled in the study once the subject has signed the informed consent and a Swan-Ganz thermodilution pulmonary artery catheter has been deployed, a FloTrac has been connected, the ClearSight finger cuff has been attached or ForeSight Elite sensors have been placed. The Study ID will be a 6-digit number, the first three numbers will identify the site, and the second set of numbers will identify the subject identification number.

A Swan-Ganz catheter, FloTrac transducer, ClearSight finger cuff and ForeSight Elite sensors will be placed prior to the start of the catheterization procedure. Intermittent cardiac output and other hemodynamic parameters will be collected throughout the duration of the procedure and analyzed according to the Statistical Analysis Plan.

Data collected in this study will support in expanding the current indications of Swan-Ganz, FloTrac and ClearSight into the pediatric population.

This study will be conducted in a manner that is consistent with the applicable regulations and in accordance with current Good Clinical Practice (GCP).

POGO Study	
Study #2019-08	

5. SUBJECT SELECTION AND WITHDRAWAL

General Characteristics of the Proposed Subject Selection

Subjects 12 to 18 years of age, with planned catheterization procedure, at least 2 weeks post cardiac transplantation, who are projected to receive an arterial line and a Swan-Ganz catheter as part of the procedure/standard of care with intermittent cardiac output measures will be screened for inclusion into the Study. Only subjects meeting all inclusion criteria will be enrolled.

Prior to any Study procedures, an IRB approved informed consent form must be signed and dated by the subject or legal guardian. Subjects who have been screened but do not sign an informed consent form will not be considered enrolled and will not have any eCRFs (electronic Case Report Forms) completed.

Informed Consent

Before a subject undergoes any Study procedures, an informed consent will be obtained utilizing the IRB approved consent form. All consent procedures will be conducted in a manner that is consistent with the applicable regulations and in accordance with Good Clinical Practice (GCP).

During the consent procedure, each potential subject will be given ample time to discuss participation in the Study and to have any questions or concerns addressed by the Principal Investigator or Investigator. Each subject will be provided with a copy of the IRB approved consent.

Inclusion Criteria

- 1. Subjects who are 12 to 18 years of age
- 2. Subjects who have signed the Informed Consent Form
- 3. Subjects who are projected to receive Swan-Ganz catheter as part of procedure/standard of care with intermittent cardiac output measures
- 4. For those Subjects who have had a cardiac transplant, Subjects must be at least two weeks post cardiac transplantation
- 5. Subjects with planned pressure monitoring with an arterial line

Exclusion Criteria

- 1. Subjects with contraindications for Pulmonary Artery Catheters placement and monitoring (recurrent sepsis, or with hypercoagulopathy);
- 2. Subjects with contraindications for Arterial Line Placement;
- 3. Subjects with an extreme contraction of the smooth muscle in the arteries and arterioles in the lower arm and hand (i.e., Raynaud's Disease).
- 4. Subjects with a physical site area too limited for proper Sensor placement
- 5. Subjects with finger size less than the smallest finger cuff size
- 6. Documented ≥ moderate pulmonary hypertension (PAPm > 25mmHg, PVRI >3.0 WUxm2)
- 7. Presence of intracardiac shunting (i.e., ASD, VSD)
- 8. Aorto-pulmonary collaterals
- 9. ≥ Moderate tricuspid regurgitation, per echocardiogram criteria
- 10. > Moderate Aortic or pulmonary regurgitation, per echocardiogram criteria
- 11. Persistent cardiac arrythmias during the catheterization period (> 3min)

THIS DOCUMENT CONTAINS CONFIDENTIAL AND PROPRIETARY INFORMATION OF EDWARDS LIFESCIENCES, LLC. IT MAY NOT BE REPRODUCED OR DISCLOSED WITHOUT PRIOR WRITTEN PERMISSION FROM EDWARDS LIFESCIENCES, LLC.

 POGO Study]
Study #2019-08	

12. Vascular abnormalities of the arterial system (i.e., connective tissue disorders, mid-aortic syndrome)

Subject Screening

All eligible subjects should be screened for Study eligibility. The Investigator and/or Designee(s) at the Study site shall review the candidate's eligibility. The Study site should maintain a cumulative log of all screened subjects that are eligible in participating.

Early Withdrawal of Subjects

Subjects may voluntarily withdraw consent at any time during the study with no loss of benefit or penalty. The Investigator may withdraw any subject if they determine that continued participation in the study may be detrimental to the subject's safety and welfare. Each subject withdrawal will be documented on the appropriate eCRF.

POGO Study	
Study #2019-08	

6. STATISTICAL METHODS

Primary Effectiveness Endpoint

The primary objective of this study is to demonstrate that monitoring of cardiac output with Sawn-Ganz, FloTrac, and ClearSight system is comparable as determined by the Bland-Altman method of bias.

Sample Size Justification

Sample size consideration for bias

The bias between the matched pairs of CO measurements, as determined by the Bland-Altman method, must be smaller than the minimum clinical difference δ , which is the value that is large enough to claim difference.

The hypothesis for bias is:

H0: bias $<-\delta$ or bias $>\delta$

H1: -δ≤ bias ≤δ

H0 is the null hypothesis (i.e. the difference between matched pairs of CO values of the two systems is larger than δ), H1 is the alternative hypothesis (i.e. the difference between matched pairs of CO values of the two systems is within the range of δ). A meta-analysis conducted a comprehensive search of 21 published medical literature to assess the accuracy and precision of minimally invasive CO monitoring systems used in children when compared with CO monitoring reference methods [8]. Among the 21 studies, 19 studies (90%) showed a bias range of -0.5 to 0.5 L/min. Based on these data, the clinical minimum difference δ was set at 0.5 L/min, i.e. bias is expected to be -0.5< bias < 0.5 l/min. This value is smaller in magnitude than the 0.8 l/min floor that the US FDA had previously considered for CO comparisons. The meta-analysis also shows that 19 out of 21 published studies had standard deviation (SD) no more than 1.0 L/min.

In this study eight repeated measurements (m=8 sub samples) or sub sample sections will be taken during the cardiac catherization case, thus intra-cluster correlation ecoefficiency ICC is a factor to be considered in sample size estimation. Here $ICC = \frac{\delta_s^2}{\delta_s^2 + \delta_{ss}^2}$. δ_s^2 is the variance component of study subject. δ_{ss}^2 is the variance component of sum sample. By literature the ICC in children ranges from 0.94 to 0.98. The variation of study subject is dominant. Fixed the study subjects, the more sub-samples taken the less δ_{ss}^2 will be by a factor 1/m. This will reduce the total variance applied in sample size calculation. Using ICC=0.98, and SD=1 (Variance=1) as an example, for m=8, as an example, for m=8, the stand deviation used in sample size estimation is $SD = \sqrt{0.98 * 1 + \frac{1-0.98}{8}} = 0.991211$..

The sample size calculation for this hypothesis is based on the one-sample t-test for equivalence. The desired outcome is to reject the null hypothesis at the 0.05 significance level. For this equivalence test of bias, two comparisons will be performed: FloTrac vs Swan-Ganz and ClearSight vs Swan-Ganz. In order to preserve the overall type 1 error rate at 0.05, the Bonferroni Correction will be used to adjust for multiple comparisons.

THIS DOCUMENT CONTAINS CONFIDENTIAL AND PROPRIETARY INFORMATION OF EDWARDS LIFESCIENCES, LLC. IT MAY NOT BE REPRODUCED OR DISCLOSED WITHOUT PRIOR WRITTEN PERMISSION FROM EDWARDS LIFESCIENCES, LLC.

POGO Study
Study #2019-08

Assuming a true mean bias of 0.0 and a SD of 1.0 l/min in the cardiac output, the sample size required for δ =0.5, alpha=0.05, and power=90% to reject the null hypothesis is 45, ignoring the ICC. After considering ICC for eight repeated measures (m=8), a sample size of 54 Subjects in needed. After considering a 34.5% rejection rate for hemodynamic instability, 10% lost to follow-up rate and 6 Roll-in Subjects for the learning curve, a total of 102 (96 evaluable Pivotal Subjects and 6 Roll-in Subjects) will be enrolled.

Adjusting for multiple comparisons, considering there will be two target devices and a reference device pairs, simultaneously, 108 total Subjects will be enrolled in this study.

Sample size consideration for percent error

The Critchley and Critchley method of percent error (PE) calculation will be compared to 30%. The Precision will be considered as acceptable if PE is less than 30 %.

The hypothesis for PE is a one-sided test:

H0: PE > 30%H1: PE $\leq 30\%$

The sample size calculation for this hypothesis was based on the one-sided T-test. The desired outcome is to reject the null hypothesis at the 0.05 significance level. Assuming a true mean of 30% and a conservative SD assumption of 70%, the sample size required for power=90% to reject the null hypothesis is 49.

Because the study is designed with sub samples (repeated measurements) or sub sample sections (m= 8), ICC is a factor needing to be considered in the sample size estimation. When eight repeated measures (m=8) are performed, the SD=69.38%. The corresponding sample size necessary is 49.

For PE, a sample size of n=60 will be used in the study design, after considering two pairwise comparisons between 2 devices with a reference device. In addition, after considering a 34.5% rejection rate for hemodynamic instability, 10% lost to follow-up rate, 102 evaluable subjects will be targeted. To account for the learning curve and 6 additional Roll-in Subjects will be enrolled, totaling 108 Subjects enrolled in the study.

Calculation of Cardiac Index (CI)

Adjusting cardiac output (CO) with study subject body surface area (BSA) results in the derivation of cardiac index (CI). This adjustment for body surface area, in the study pediatric population (12 to 18 years old), will result in a smaller bias and percent error between test device and reference device. The standard deviation estimate will also be smaller, at the same scale, thus, the sample size estimate decreases. Sample size estimates for bias and percent error for CI is detailed in the SAP.

THIS DOCUMENT CONTAINS CONFIDENTIAL AND PROPRIETARY INFORMATION OF EDWARDS LIFESCIENCES, LLC. IT MAY NOT BE REPRODUCED OR DISCLOSED WITHOUT PRIOR WRITTEN PERMISSION FROM EDWARDS LIFESCIENCES, LLC.

POGO Study		
Study #2019-08		

Primary Safety Endpoint

The primary safety endpoint is to assess all serious intraoperative and post-operative adverse events through 30 days, including serious device-related events.

Analysis Populations

All enrolled subjects with evaluable data will be included in the analysis of effectiveness endpoint, and all enrolled subjects will be included in the analysis of safety endpoint.

The analysis set is composed of all evaluable subjects with valid CO matched pair measurements from the target medical device system (FloTrac and ClearSight systems) and the reference medical device system (the Swan-Ganz thermodilution pulmonary artery catheter).

Evaluable subjects are those with non-rejected intermittent thermodilutions who have completed the 30-day telephone follow up period.

Analysis Methods

The primary effectiveness endpoints will be accessed using the testing method described in the Sample Size Justification section. Additionally, descriptive statistics will be used to summarize data. Mean, SD, median, 25th (Q1) and 75th (Q3) percentiles, minimum, and maximum will be reported for continuous variables; frequency and percentage of subjects will be reported for categorical variables. Further details of the analysis method will be described in the Statistical Analysis Plan for this study.

Secondary Effectiveness Endpoint

The secondary effectiveness endpoint is to demonstrate that monitoring of cardiac output (CO) with Swan-Ganz, FloTrac and ClearSight is comparable, as determined by the Critchley and Critchley method of percent error.

Additional Evaluations

The following additional evaluations will be included and considered exploratory:

- Comparison analysis of CI as determined by the Bland-Altman method of bias calculation with confidence intervals
- Comparison analysis of CI as determined by the Critchley and Critchley method of percent error calculation with confidence intervals
- Subgroup analysis of primary and secondary endpoint by age stratification
- Subgroup analysis of primary and secondary endpoint by gender
- Subgroup analysis of primary and secondary endpoint by race
- Subgroup analysis of primary and secondary endpoint by site

THIS DOCUMENT CONTAINS CONFIDENTIAL AND PROPRIETARY INFORMATION OF EDWARDS LIFESCIENCES, LLC. IT MAY NOT BE REPRODUCED OR DISCLOSED WITHOUT PRIOR WRITTEN PERMISSION FROM EDWARDS LIFESCIENCES, LLC.

POGO Study	
Study #2019-08	

- Comparison of cardiac output from FloTrac, ClearSight and Swan-Ganz technologies to the Fick principle
- Evaluation of hemodynamic parameters that are collected by the FloTrac, ClearSight, Swan-Ganz technologies, including:
 - Cardiac Output (CO)
 - Cardiac Index (CI)
 - o Pulse Rate (PR)
 - Stroke Volume (SV)
- Evaluation of other hemodynamic parameters that will be collected during the catherization procedure, as prespecified in the SAP

POGO Study	
Study #2019-08	

7. RECEIVING, STORAGE, AND RETURN OF DEVICES

Receipt of Device Supplies

A packing list will accompany all device shipments. This list will include the inventoried product with receipt date and investigator and/or designee signature.

Storage

The HemoSphere advanced monitoring platform and all investigational devices for use in this study shall be stored in a secure and clean area complying with the storage instructions provided in the labeling.

Device Accountability

The Investigator and/or delegated-study personnel shall keep records documenting the receipt, use, return, and disposal of the devices. Only the Investigator, delegated-Study Personnel and/or designee(s) (i.e., Assisting Clinician(s)) may use the devices. The Investigator will supervise the used of the device in Study subjects. The Study site shall account for which system/device was used for which subject as well as for the return of the system/device.

Return of Device

The Principal Investigator is responsible for returning the unused product back to the Sponsor.

POGO Study	
Study #2019-08	

8. SCHEDULE OF EVENTS & PROCEDURES

Schedule of Events

Lifesciences Corporation.

The following matrix shows the scheduled assessments through the end of the Study (30-Day Follow Up).

Study Procedure / Exam	Subject Screening	Procedure	Discharge	30-Day Follow Up (±14 Days)
Obtain Informed Consent	X	7 10000.010	2.00.10.180	(==: ==;
Perform Inclusion / Exclusion Evaluation	Х			
Obtain Medical History / Subject Demographics ¹	Х			
Assign Subject ID		Х		
Enter Subject Data into Monitor		Х		
Vital Signs		Х		
Monitoring Duration		Х		
Data download from Monitor		Х		
Obtain Fluid and Vasoactive Medication Administration Record ²		Х		
Complete eCRFs	Х	Х	Х	Х
Record Adverse Events, if applicable		Х	Х	Х
Phone Contact 30-day follow up / Mortality Determination				х

The duration of individual study participation is expected to be 30 days (±14 days) after procedure.

Data collection will occur during the study via the HemoSphere platform and electronic case report forms (eCRFs). The 30-day follow-up phone contact will be recorded on the applicable eCRF.

2019-08 Page **26** of **52 CONFIDENTIAL**

¹ Medical History / Subject Demographics / Surgical and Clinician Demographics can be obtained prior to procedure, either at the screening visit or on the day of procedure.

² Can be collected via the hospital record system anytime on the day of procedure or thereafter.

THIS DOCUMENT CONTAINS CONFIDENTIAL AND PROPRIETARY INFORMATION OF EDWARDS LIFESCIENCES, LLC. IT MAY NOT BE REPRODUCED OR DISCLOSED WITHOUT PRIOR WRITTEN PERMISSION FROM EDWARDS LIFESCIENCES, LLC.

Edwards Lifesciences, Edwards, the stylized E logo, HemoSphere, Swan-Ganz, FloTrac, ClearSight and ForeSight Elite are trademarks of Edwards

P(OGO Study	ĺ
St	tudy #2019-08	ì

Intermittent Thermal Dilution Assessment(s)

Using the Swan-Ganz thermodilution pulmonary artery catheter, two series of four (4) intermittent dilutions should be administered by the Investigator while in the cath lab. The dilution curves are analyzed and averaged to give one (1) CO value.

CO measured by the ClearSight and FloTrac systems will be simultaneously compared with the CO measured by the Swan-Ganz catheter using the thermodilution method. There will be 2 sets of 4 measurements recorded over a 30-second interval, during the Swan-Ganz thermodilution bolus injection. Those 4 measurements will be pair-matched by time in the ClearSight and FloTrac systems. The same number of measurements that will be recorded during the Swan-Ganz thermodilution will be recorded for the ClearSight and FloTrac devices. The following thermodilution procedure will be used:

A 10 ml sample of iced glucose solution (5%) will be drawn through an iced injectate container (CO-SET+ or any other container that meets the requirements, as determined by the investigator) and injected in a steady manner. Four TD CO determinations will output, preferably within 5 minutes. From there, three values, will be averaged to obtain one single value. Each thermodilution curve will be visually checked before acceptance. The dilution curve will be automatically corrected for the temperature of the blood and of the injectate measured at the entrance of the catheter lumen. Values for temperatures will be stored together with the thermodilution values. The entire series of four thermodilution estimates will be rejected if, during an injection, the HemoSphere advanced monitor displays an alert signal, if the injectate temperature is above 10 °C, or when the curve of the dilution is abnormal. In case of rejection, the entire series of four thermodilutions will be repeated.

Hemodynamics and respiratory rate must be stable during the TD series, since variability violates the assumption of stability that is required for the TD technique. Sponsor-instream review of the TD series will occur after each catheterization to determine if hemodynamic variability occurred and the site team will be retrained on the importance of conducting the TD technique during hemodynamic stability.

Clinical Study Completion or Early Termination

The IRB will be notified upon completion or premature termination of the study. Edwards retains the right to suspend or prematurely terminate this clinical study at any time.

If suspicion of an unacceptable risk to subjects arises during the clinical investigation, or when so instructed by the IRB or regulatory authorities, Edwards shall suspend the study while the risk is assessed by the Data Safety Monitoring Board (DSMB). Edwards shall terminate the clinical investigation if an unacceptable risk is confirmed.

Protocol Deviation

Any deviations from the protocol will be documented on the protocol deviation eCRF. The Investigator/or Designee shall be responsible for the reporting of any deviations deemed reportable to the IRB.

THIS DOCUMENT CONTAINS CONFIDENTIAL AND PROPRIETARY INFORMATION OF EDWARDS LIFESCIENCES, LLC. IT MAY NOT BE REPRODUCED OR DISCLOSED WITHOUT PRIOR WRITTEN PERMISSION FROM EDWARDS LIFESCIENCES, LLC.

POGO Study
Study #2019-08

Deviations shall be reported to the Sponsor, regardless of whether they are medically justifiable, pre-approved by the sponsor, or taken to protect the subject in an emergency. Subject-specific deviations will be reported on the appropriate eCRF.

Non-subject specific deviations (e.g. unauthorized use of a device outside the study, etc.) will be reported in writing. The investigator will also adhere to procedures for reporting study and subject specific deviations to their IRB in accordance with their specific IRB's reporting policies and procedures.

POGO Study		
Study #2019-08		

Changes to the Protocol

Changes to the research covered by this protocol must be implemented by formal protocol amendment. All amendments to the protocol must be initiated by the Sponsor.

Protocol amendments must not be implemented without prior IRB approval. Documentation of amendment approval by the Investigator and IRB or IEC must be provided to the Sponsor or its authorized representative. When the change(s) involve only logistic or administrative aspects of the study, the IRB only needs to be notified.

POGO Study	
Study #2019-08	

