10. REPORTABLE EVENTS

Recording and Reporting of Adverse Events

The Investigator and/or Designee(s) will determine whether any adverse events (AEs) have occurred. An AE is defined as any untoward medical occurrence in a clinical Study of an Investigational Device regardless of the causal relationship of the problem with the device or, if applicable, other Study treatment or diagnostic product(s). Information for AEs with the study devices will be collected from the time a subject begins the study procedure and is exposed to Study products. AEs will also be collected during surgical intervention, post intervention, discharge and through the 30-day follow-up. AEs may be volunteered by subjects, clinicians, elicited from questioning by Investigator and/or Designee(s), or collected via observation. When a device or study related AE is suspected all available event information and will be provided to the Clinical Events Committee.

Once an AE/SAE/UADE is confirmed as such, event, date of onset, severity, duration, treatment (if required), resolution (or ongoing), assessment of seriousness, relationship to Study procedure and relationship to device will be recorded on the appropriate eCRF or SAE Report Form and submitted as necessary by the Investigator and/or Designee(s). Any suspected AEs related to the Investigational Device or Study procedure must be reported to the Sponsor or designee within 5 working days of first awareness of the event.

Recording and Reporting of Adverse Device Effects

An adverse device effect (ADE) is defined as an AE related to the use of an investigational medical device. This definition includes AEs resulting from insufficient or inadequate instructions for use, deployment, implantation, installation or operation, or any malfunction of the investigation device. It also includes any AE resulting from use error or from intentional misuse of the Investigational Device.

Causality of relationship to the Investigational Device will be judged by the Investigator, and reviewed independently by the Clinical Events Committee, as follows:

Not related:

• An event is clearly not and cannot be related to the Investigational Device. Reporting is not required per protocol unless the event was related to the Investigational Device or Study.

Possibly Related:

• A relationship may exist but could have been produced by another cause (e.g., treatment, condition).

Related:

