UADEs must be reported to the Sponsor or designee within 24 hours and submitted to the reviewing IRB as soon as possible, but in no event later than 10 working days after the Investigator first learns of the effect. All AEs related to the Investigational Device or Study will be reviewed by the Investigator and/or Designee(s) and Sponsor. These AEs will be followed until they are adequately resolved, explained by the Investigator and/or Designee(s), until subject has completed follow-up or been withdrawn from the Study.

POGO Study	
Study #2019-08	

Recording and Reporting of Deaths

Events resulting in death during the subject's enrollment in this Study are not expected to occur as a result of participation in the Study. In the event of subject death; however, every reasonable effort should be made to obtain a copy of the autopsy report and/or death summary. Information on the date and cause of death and its relationship to the Study device will be determined by the Investigator and/or Designee and recorded on the appropriate AE eCRF and submitted on an SAE Report Form as necessary.

Recording and Reporting of Adverse Events Associated with Commercial Components

Any adverse event associated with an FDA cleared component will be recorded as a device complaint and reported via the MDR program (21 CFR Part 803). Complaints will also be reported to the IRB in accordance with each IRB's requirements. Device complaints should be reported to the Sponsor as soon as the site becomes aware of the complaint.

Recording and Reporting of Pre-Existing Conditions

Pre-existing medical conditions and symptoms due to pre-existing medical conditions, surgery or admission to ICU will not be recorded as adverse events. The admission of a critically ill patient in the intensive care unit is commonly due to one or several serious medical conditions and/or a major surgery, which may cause changes and abnormalities of blood chemistry, diagnostic and physiological parameters. In the event there is a deterioration of a pre-existing medical condition or symptoms due to the use of the Study products or a Study related procedure, then the review of the event will be initiated, and an AE will be recorded if it meets the definition. Any events occurring prior to the study procedure will be recorded as medical history.

Reporting Adverse Events to the FDA

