Interim monitoring visits (onsite or remote) will be conducted to evaluate the progress of the study, verify the rights, well-being, and protection of the patients, and verify that the reported clinical study data is accurate, complete and verifiable from the electronic medical records and source documents. Monitoring visits will be made in accordance with the Monitoring Plan.

Site Close-Out Visit

The Investigator will be notified in writing upon termination or completion of the Study. The Sponsor retains the right to suspend or prematurely terminate this clinical investigation at any time. Upon completion or premature termination of the Study, the Study monitor will perform a close-out visit.

THIS DOCUMENT CONTAINS CONFIDENTIAL AND PROPRIETARY INFORMATION OF EDWARDS LIFESCIENCES, LLC. IT MAY NOT BE REPRODUCED OR DISCLOSED WITHOUT PRIOR WRITTEN PERMISSION FROM EDWARDS LIFESCIENCES, LLC.

POGO Study	
Study #2019-08	

A site will be considered closed when the following criteria are met:

- Last subject completes 30-day follow-up
- All data queries are resolved
- A site closeout visit is completed
- The IRB is notified in writing of site and study closure in accordance with their requirements

Auditing and Inspecting

In the event that audits are initiated by the Sponsor or national/international regulatory authorities, the Investigator shall allow access to the original medical records and provide all requested information, as applicable. The Investigator will permit Study-related monitoring, audits, and inspections by the Research Quality Assurance Office, IRB, the Sponsor, and government regulatory bodies, of all Study related documents (e.g. source documents, regulatory documents, data collection instruments, Study data etc.). The Investigator will ensure the capability for inspections of applicable Study-related facilities (e.g. pharmacy, diagnostic laboratory, etc.).

POGO Study	
Study #2019-08	

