5.2. Evaluable Subject

An evaluable subject is one who has valid CO pair measurements that were not rejected and also has completed the 30-Day follow up.

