7.5 Study Procedure

The schedule of events is illustrated in the following table.

Study Procedure / Exam	Subject Screening	Procedure	30-Day Follow Up (±14 Days)
Obtain Informed Consent	Χ		
Perform Inclusion / Exclusion Evaluation	Х		
Obtain Medical History / Subject Demographics ¹	Х		
Assign Subject ID		X	
Enter Subject Data into Monitor		X	
Vital Signs		X	
Monitoring Duration		X	
Data download from Monitor		X	
Obtain Fluid and Vasoactive		V	
Medication Administration Record ²		X	
Record Adverse Events, if applicable		X	Х
Phone Contact 30-day follow up / Mortality Determination			Х

¹ Medical History / Subject Demographics / Surgical and Clinician Demographics can be obtained prior to procedure, either at the screening visit or on the day of procedure.

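### The ±14-day window on the final call means that observation through day 30, which the primary safety endpoint requires, is not guaranteed, and no day-30 cut-off is stated

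*Combined protocol and SAP*

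**What the plan says.** Protocol section 6 (Primary Safety Endpoint) fixes the horizon: "The primary safety endpoint is to assess all serious intraoperative and post-operative adverse events through 30 days, including serious device-related events". The synopsis, protocol section 3 and SAP section 3 give the same horizon.

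Protocol section 8 introduces its schedule with "The following matrix shows the scheduled assessments through the end of the Study (30-Day Follow Up", so that contact closes the study for the subject. It then states: "The duration of individual study participation is expected to be 30 days (±14 days) after procedure". The schedule has columns for screening, procedure, discharge and the follow-up call. The call is the only contact after discharge and the only entry for determining mortality. SAP section 7.5 repeats the window in its own schedule: "30-Day Follow Up (±14 Days".

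Four other places bear on when observation ends:

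- Protocol section 10, on collection of events: "AEs will also be collected during surgical intervention, post intervention, discharge and through the 30-day follow-up".
- Protocol section 10, on how long events related to the device or study are followed; one permitted end point is "until subject has completed follow-up or been withdrawn from the Study".
- Protocol section 16, on closing a site; the follow-up condition is "Last subject completes 30-day follow-up".
- Protocol section 6 (Analysis Populations) puts all enrolled subjects in the safety analysis, and SAP sections 9.1 and 9.2 summarise events as frequencies and percentages.

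**The concern.** For a repeatable measurement, a symmetric visit window is usually harmless: the value is simply taken a little early or late. Here the call is how a cumulative endpoint is ascertained after discharge. Moving it earlier removes follow-up time, and moving it later adds follow-up time unless the count is cut at day 30.

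The endpoint is written with a fixed horizon, but data collection has a horizon that varies between subjects. A subject last contacted on day 16 stays in the denominator and is treated as event-free to day 30, though nothing is known about the last two weeks. A subject called on day 44 can contribute an event that falls outside the endpoint. With at most 108 subjects, a few events settle the reported percentage, so call timing alone could move it visibly. This is a named primary endpoint, offered in support of a paediatric indication, and the DSMB reviews it.

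**Working it through.** There is no figure in the plan to reproduce. The check sets the endpoint against the window and then illustrates the size.

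**Inputs from the documents.** Horizon: 30 days (protocol section 6). Window: ±14 days (protocol section 8, SAP section 7.5). Safety population: all enrolled, up to 108 (protocol sections 4 and 6).

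**Window arithmetic.**
- Earliest compliant call: 30 − 14 = day 16.
- Latest compliant call: 30 + 14 = day 44.
- Unobserved after a day-16 call: days 17 to 30, which is 14 days; 14/30 = 46.7%.
- Outside the endpoint but observable at a day-44 call: days 31 to 44, also 14 days.

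**Is the gap recovered elsewhere?** Event collection ends with the call, related events need not be followed beyond completed follow-up, and a site may close after its last call. None of these provisions refers to day 30 having passed. SAP section 9 has no onset cut-off, no censoring and no adjustment for length of follow-up. Nothing requires a second contact or chart review after an early call.

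**Illustration 1: lost follow-up time.** Assume calls are spread evenly over the 29 days from 16 to 44. The documents give no call-time distribution.
- Calls before day 30: 14/29 = 48%.
- Mean unobserved days per subject: (14 + 13 + … + 1)/29 = 105/29 = 3.6 days, or 3.6/30 = 12% of the 30-day period.
- Mean call day: 30.

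**Illustration 2: effect on the percentage.** Assume a constant hazard, so that risk by day t = 1 − (1 − p)^(t/30), where p is the true 30-day risk. The documents give no expected rate, so a range of p is shown.

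| True 30-day risk | All calls day 16 | All calls day 44, no cut-off | Even spread, no cut-off | Even spread, cut at day 30 |
|---|---|---|---|---|
| 2% | 1.1% | 2.9% | 2.0% | 1.8% |
| 5% | 2.7% | 7.2% | 5.0% | 4.4% |
| 10% | 5.5% | 14.3% | 10.0% | 8.8% |
| 20% | 11.2% | 27.9% | 19.8% | 17.8% |

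In 108 subjects at a true risk of 5%, the expected number with an event is 108 × 0.05 = 5.4 by day 30. It is 2.9 if all calls are on day 16, and 7.8 if all are on day 44 with no cut-off.

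The second and third columns are extremes. The fourth shows early and late calls nearly cancelling when no cut-off is applied. The fifth shows that adding a cut-off while keeping the two-sided window gives a net loss of about 11% to 12% of events under these assumptions (for example 1 − 4.4/5 = 12%).

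**The case against.** Five points can be made on the other side.

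**The gap is permitted, not certain.** Day 30 is the target and actual call dates are unknown. Events may also reach the site by other routes, since protocol section 10 accepts reports volunteered by subjects or clinicians. This stands, and it is why the point says not guaranteed. But nothing requires such a report after an early call.

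**Downward bias does not follow.** A reader might infer that the reported rate must be too low. The documents do not support that. Without a cut-off, late calls add events just as early calls lose them; with evenly spread calls the two roughly cancel. A net downward error needs mostly early calls, or a day-30 cut-off combined with the present window.

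**The endpoint might be visit-based.** Protocol section 10 collects events up to the follow-up contact, and SAP section 9.1 can be read the same way. On that reading endpoint and window agree. But follow-up would then run from 16 to 44 days and the percentages would still not be 30-day rates, so the wording needs reconciling either way.

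**Serious events may cluster near the procedure.** Most of the listed device risks concern placing or wearing the device. If so, the loss is smaller than the constant-hazard figures. It need not be nil: protocol section 9 also lists 30-day mortality, sepsis and wound infection.

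**The endpoint is descriptive.** There is no hypothesis, performance goal or comparator, and the window cannot alter any cardiac output value. This stands and limits the severity.

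A reader might also cite SAP section 5.2, where an evaluable subject is one who "also has completed the 30-Day follow up". That definition governs the effectiveness set. The safety denominator is all enrolled subjects, so it does not bear on this point.

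**Conclusion.** The point holds in this form: the plan does not guarantee observation through day 30 and does not say which events count when the call falls on another day. A compliant early call can leave up to 14 of 30 days (47%) unobserved, and a compliant late call can add up to 14 days beyond the endpoint. Both figures follow from the window alone. The resulting percentages would rest on follow-up of 16 to 44 days.

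The 12% of follow-up time lost and the risk table depend on assumed call timing, and the table also on a constant hazard and assumed true risks. They show scale and are not estimates for this study. The number of subjects affected and the net direction of the error cannot be known from the documents. The matter should be corrected because the endpoint is primary and the correction is cheap. It does not touch the effectiveness conclusions.

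**What to change.** 1. In protocol section 8 and SAP section 7.5, set the window for the final call to day 30 to day 44. Alternatively, keep earlier contacts but require a repeat call or chart check on or after day 30 following any of them. Change the stated duration of participation to match.
2. In SAP section 9, state that only events with onset on or before day 30 count toward the primary safety endpoint, and list later events separately.

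Both parts are needed. A cut-off alone leaves the early gap, and a later window alone lets in events after day 30. For every subject who completes the contact, the unobserved part of the 30-day period falls from up to 14 days to 0.

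The cost is that some calls are made later, and the protocol must be amended with IRB approval before the change takes effect. Sample size and cardiac output measurement are unaffected.
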